3.6 Treatment Groups for Analysis

Data analyses and summary tables by study group will be conducted and displayed as follows:

- The summary of immunogenicity response TNA NF₅₀ will be presented for each of three lots of AV7909 study groups, AV7909 group (three lots pooled), and BioThrax group.
- For the AV7909 lot consistency analysis in terms of GMT ratio for TNA NF₅₀, data summary and analysis results will be presented for each of three lots of AV7909 study groups.
- For AV7909 immunogenicity on Days 64 and 29, data summary and analysis results will be tabulated for the combined AV7909 group (three lots pooled).
- For non-inferiority of AV7909 vs BioThrax on Day 64, data summary and analysis results will be tabulated with two groups: AV7909 (three lots pooled) and BioThrax group.
- All safety analyses (i.e., AEs), data summary and analysis results will be tabulated with two groups: AV7909 (three lots pooled) and BioThrax group.

Otherwise, data summary results will be displayed for each of three lots of AV7909 study groups, AV7909 group (three lots pooled), and BioThrax group. An overall ‘Total’ column will be included for participant disposition, demographics and baseline characteristics, protocol deviations, and exposure to study vaccinations.

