10.5. Immunogenicity Analysis

Immunogenicity results by visit for each study group (AV7909 Lot 1, AV7909 Lot 2, AV7909 Lot 3, and BioThrax) and combined AV7909 group (three lots pooled) will include:

- Descriptive summaries (n, mean, SD, median, minimum, and maximum) of TNA NF₅₀ values
- Geometric mean titer and corresponding 95% CIs for TNA NF₅₀ values calculated by taking the anti-logarithms of the mean and 95% CIs for log₁₀ TNA NF₅₀

- Proportion of participants with TNA NF₅₀ ≥ 0.56 (also TNA NF₅₀ ≥ 0.29 and TNA NF₅₀ ≥ 0.15) with associated 95% CI (exact Clopper Pearson confidence limit).

Line plots of GMT with associated 95% CI for TNA NF₅₀ by study group over time will be provided. Reverse cumulative distribution curve for TNA NF₅₀ values on Day 29 and 64 will be provided.

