10.6.2. Adverse Events

All AEs will be coded to SOC and PT according to MedDRA. Treatment-emergent adverse events (TEAEs) are defined as AEs that present after the initiation of treatment or any AEs already present that worsen in either intensity or frequency following treatment. The incidences of TEAEs will be presented in tabular form by summary categories of TEAEs (eg, any TEAEs, any drug-related TEAEs, any Grade 3 or 4 TEAEs) and using the MedDRA coded terms of SOC and PT overall, by $\geq 2\%$ incidence in either group, and by severity (toxicity grade), seriousness, relationship to IP, and outcome (death, discontinuation of IP, study withdrawal) for each study group. A separate tabulation by MedDRA SOC and PT will be provided of treatment-emergent AESIs determined to be of autoimmune etiology based on decision of the DSMB. Participants having the same TEAE more than once will be counted in tabulations once for each PT and once within each SOC at the maximum severity and relatedness. An additional tabulation will be provided of TEAE incidences by MedDRA PT in decreasing frequency of the AV7909 (three lots pooled) group relative to the incidences in the BioThrax group. The incidences of AEs from the time of the first vaccination on Day 1 through Day 64, as well as incidences of AEs reported from Day 1 and up to Month 13 will be provided for AV7909 (three lots pooled) and BioThrax groups.

The proportions of participants with treatment-emergent SAEs and AESIs and associated two-sided 95% CIs will be provided for AV7909 (three lots pooled) and BioThrax groups. The relative risks for treatment-emergent SAEs and AESIs between AV7909 and BioThrax groups and associated 95% CIs will also be provided. No formal hypotheses testing will be conducted.

Separate listings will be prepared for AEs, deaths, SAEs, TEAEs leading to discontinuation of IP or study withdrawal, and AESIs.

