2.4 Sample Size and Power Considerations

Sample size for this study is based primarily on safety considerations. The total sample size across all three AV7909 study groups is set at 3300 participants. Allowing a 10% drop-out rate, this sample size for safety (3000) is sufficient to detect, with 95% probability, an AE rate of 1:1000, or 0.1%.

It is expected that more participants will be excluded from the immunogenicity analysis population (Per Protocol [PP] Population; refer to [Section 3.2](#)) than excluded from the Safety Population. A 25% exclusion rate from the PP Population is assumed. Thus, the PP Population will include approximately 800 participants for each AV7909 group (2400 participants total) and 400 participants for the BioThrax group.

Even under the best manufacturing practices, between-lot variation exists and will be considered normal. It is assumed that the lot-to-lot geometric mean titer (GMT) ratio could be as low as 0.6 based on Emergent's experience with the BioThrax vaccine. Conservatively, the largest GMT ratio between two out of three lots is assumed to be 1.5. Assuming a coefficient of variation of 100% (slightly larger than the observed 91% in the phase 2 study, EBS.AVA.208), this study has >99% power to demonstrate lot consistency with the pre-specified equivalence bounds ([0.5, 2.0]) in terms of GMT ratio for TNA NF₅₀ at Day 64.

Based on the combined phase 1 and phase 2 data, the proportion of participants receiving two doses of AV7909 on Day 1 and Day 15 with TNA NF₅₀ at Day 64 over 0.56 is approximately 63% with lower 95% CI of 50% (total n = 54). Even assuming a conservative 50%, the study provides >99% power of rejecting the null hypothesis of 40% in each of the three AV7909 lots and in the combined AV7909 group (three lots pooled).

For the non-inferiority endpoint, among participants (n = 184) receiving BioThrax PEP regimen (3 doses, SC) in the EBS.AVA.006 study, 93.5% had TNA NF₅₀ values above 0.29 at Day 64. In the AV7909 phase 2 study (EBS.AVA.208), 86.5% of participants (n = 37) had TNA NF₅₀ above 0.29 at Day 64. Assuming a rate of 93% for the BioThrax group and 83% for the AV7909 group, the sample sizes of 400 and 2400 provide approximately 98% power to demonstrate non-inferiority of the two-dose AV7909 IM regimen to the three-dose BioThrax SC regimen at Day 64 with a non-inferiority margin of 15%.

The sample size calculation was performed using PROC POWER in SAS/STAT 9.4.

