2.5 Randomization and Blinding

2.5.1 Randomization

At the Day 1 (randomization) visit, after the PI has confirmed that the participant meets all of the inclusion criteria and none of the exclusion criteria, the participant will be randomly assigned to one of the four study groups with the ratio of 2:2:2:1 (block size of 7) via an interactive voice and/or web response system (IxRS). Randomization will be stratified by site. Racial distribution will be monitored among recruited participants. Participants who are randomized and do not receive vaccination on the same day will be withdrawn from the study. Randomized participants who withdraw from the study for any reason will not be replaced in this trial.

A randomization plan describing the method of treatment allocation and implementation of this method will be prepared and finalized prior to randomization of the first participant.

A screen failure is a participant from whom informed consent is obtained and documented in writing, but who is not subsequently randomized to study treatment. Participants who are screen failures are permitted to be rescreened one time (only) according to the PI's discretion. If a participant is rescreened, a new subject ID will be assigned. To link records to the same participant, the participant's previous subject ID will be recorded in the eCRF along with the new subject ID. Participants who complete the rescreening and are randomized in the study will not be considered screen failures.

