7 SAFETY ANALYSIS

All safety data will be presented based on the Safety Population. Data summaries will be tabulated by two treatment groups, AV7909 (three lots pooled) and BioThrax group. Continuous variables will be summarized using number of participants (n), mean, SD, median, minimum, and maximum; categorical variables will be summarized by the number (frequency) and percentage in each category.

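### No safety summary table shows the three AV7909 lots separately, although each lot is a randomised arm and the protocol is mixed on whether by-lot tables are intended

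*SAP*

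**What the plan says.** **SAP.** Section 2.5.1 has participants "randomly assigned to one of the four study groups with the ratio of 2:2:2:1 (block size of 7"), so Lots 1, 2 and 3 are three separate arms. For safety, section 3.6 says: "All safety analyses (i.e., AEs), data summary and analysis results will be tabulated with two groups: AV7909 (three lots pooled) and BioThrax group". The opening of section 7 repeats it: "Data summaries will be tabulated by two treatment groups, AV7909 (three lots pooled) and BioThrax group". Sections 7.1 to 7.8 add no by-lot safety summary. For output not assigned to particular groups, section 3.6 does the opposite: "Otherwise, data summary results will be displayed for each of three lots of AV7909 study groups, AV7909 group (three lots pooled), and BioThrax group".

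**Protocol.** It is not uniform.
- Section 10.2 bases safety analyses on BioThrax and the combined AV7909 groups. Parts of 10.6.2 name the three lots pooled, including those on proportions and relative risks for serious adverse events (SAEs) and AESIs. Section 10.7 pools the lots for subgroups.
- Another sentence of 10.6.2 asks for TEAE tables by severity, seriousness, "relationship to IP, and outcome (death, discontinuation of IP, study withdrawal) for each study group". The synopsis uses the same term for laboratory values, vital signs and the e-diary.
- Section 10.5 shows what the term covers elsewhere: results "for each study group (AV7909 Lot 1, AV7909 Lot 2, AV7909 Lot 3, and BioThrax").

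**The concern.** Lot consistency is a primary objective, but both of its endpoints are Day 64 TNA measures. Meeting them says nothing directly about whether the lots produce similar reactions. Protocol 4.3 reports that, in the phase 1b study, raising CPG 7909 from 0.25 mg to 0.5 mg increased local and systemic reactions without improving immunogenicity. By the sponsor's own account, then, reactogenicity can move while the antibody response does not.

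If one lot were more reactogenic, the planned safety tables would show only a modestly raised AV7909 rate, with nothing to indicate that it came from one lot. The comparison with BioThrax would rest on an unexamined assumption that the lots are alike for safety. Randomisation has already supplied the data to look at this; the tables do not use them.

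**Working it through.** **Inputs from the documents**
- AV7909 sample size (SAP 2.4): "The total sample size across all three AV7909 study groups is set at 3300 participants", that is 1100 per lot; BioThrax 550 (SAP Table 2).
- "Allowing a 10% drop-out rate" (SAP 2.4). The plan rounds the AV7909 safety number to 3000. I use 1000 per lot and 500 for BioThrax.
- Thirteen solicited reactions: nine injection-site and four systemic (Protocol 8.3.5.1).

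**Assumed:** the event rates in steps 3 to 5. The documents give no safety rates by lot.

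**1. The plan's own figure.** Probability of at least one event = 1 − (1 − p)^n. With p = 0.001 and n = 3000, 1 − 0.999^3000 = 0.950. With exactly 3300 × 0.9 = 2970, it is 0.949. The stated 95% reproduces, and it applies to the pooled group.

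**2. The same figure for one lot.** 1 − 0.999^1000 = 0.632. The rate detectable with 95% probability is 1 − 0.05^(1/1000) = 0.30%, against 0.10% pooled. By-lot columns are therefore weak for rare events.

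**3. Dilution.** With equal lots, two at rate b and one at rate a, the pooled rate is (2b + a)/3. The pooled excess over b is (a − b)/3, one third of the lot's excess. For b = 2% and a = 4%, the expected counts are 20, 20 and 40 in 1000 each, and the pooled column shows 80/3000 = 2.7%. A rate doubled in one lot appears as a 1.33-fold pooled rate.

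**4. How much lot information the tables forgo.** Normal-approximation power, two-sided 0.05: Φ((d − 1.96·SE0)/SE1), where d is the difference, SE0 uses the common rate and SE1 the separate rates.
- Affected lot (1000) against the other two (2000), 4% v 2%: d = 0.0200, SE0 = 0.00624, SE1 = 0.00694, giving Φ(1.12) = 87%.
- Pooled AV7909 (3000) against BioThrax (500) at the base rate, 2.67% v 2%: d = 0.00667, SE0 = 0.00765, SE1 = 0.00692, giving Φ(−1.20) = 11%.

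| Base v affected lot | Pooled rate | Lot v other two lots | Pooled v BioThrax |
|---|---|---|---|
| 1% v 2% | 1.3% | 60% | 7% |
| 2% v 4% | 2.7% | 87% | 11% |
| 3% v 6% | 4.0% | 96% | 16% |
| 0.1% v 0.3% | 0.17% | 28% | 3% |

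The first comparison assumes one knows which lot to single out. A 2-df chi-square across the three lots, which does not, has by simulation 49%, 80% and 94% power for the first three rows at 1000 per lot, and 53%, 84% and 96% at 1100.

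**5. Multiplicity.** If all thirteen reactions were tested at 0.05 after one vaccination and the tests were independent, the chance of at least one false signal would be 1 − 0.95^13 = 49%. At 0.05/13 per test, simulated power for 2% v 4% at 1100 per lot falls from 84% to about 55%. The powers in step 4 therefore indicate how much information the data hold. They are not the operating characteristics of a descriptive table.

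**The case against.** The strongest defence is that pooling is the protocol's design. Section 10.2 names the combined AV7909 group, the sample size rests on about 3000 pooled participants, and the SAE and AESI comparisons are specified as pooled. No safety endpoint is defined by lot, and safety has no formal hypothesis tests. All of this stands, and it is why the pooled comparison should remain the main one.

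Four stronger readings are tempting, and the documents do not support them.
- **That the SAP breaks a clear promise of by-lot tables.** The sentence in 10.6.2 that asks for results by study group also sets an incidence cut-off in either group, which is two-group language. The list of four groups comes from the immunogenicity section. This is an ambiguity, which the SAP resolves in line with 10.2.
- **That a lot excess disappears altogether.** One third of it remains in the pooled rate. Listings are sorted by study group. Disposition falls under the by-lot default of SAP 3.6 and includes reasons for discontinuing treatment (SAP 5.1). Protocol Table 5 makes confirmed Grade 3 or higher systemic reactions a reason to discontinue, so such an excess could surface there. That route is indirect: it does not summarise reactions, and it would miss those after the last injection.
- **That the protocol expects lots to differ in safety.** The variability discussed in Protocol 4.2 is in antibody response and supports the 0.5 to 2.0 equivalence bounds. The finding in 4.3 compares formulations, not lots. It shows that TNA need not track reactogenicity; it does not show that these lots differ.
- **That safety pooling should wait for lot consistency, as immunogenicity pooling does.** That condition is a step in the hierarchical testing sequence, and safety has no such sequence.

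The defence leaves one gap: a reader of the planned safety summaries cannot compare the lots.

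**Conclusion.** The point holds as a gap in presentation. Every safety summary is planned as pooled AV7909 against BioThrax, so none shows a lot, and a single lot's excess appears at one third of its size. The dilution follows from equal lot sizes alone; the 2% and 4% rates and the powers are illustrations. The gap matters most for solicited reactions and Grade 3 or higher TEAEs, where about 1000 per lot is informative. It matters little for rare SAEs and AESIs: at a true rate of 0.1%, a lot of 1000 has about a 63% chance of showing any event. No primary or secondary conclusion changes. This is a cheap improvement, together with a wording inconsistency in the protocol that should be settled.

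**What to change.** 1. Keep pooled AV7909 against BioThrax as the main safety comparison.
2. Add descriptive Lot 1, Lot 2 and Lot 3 columns, without tests, to the solicited-reaction tables (SAP 7.7.1) and to the overall TEAE summary, including its Grade 3 or higher rows (SAP 7.2.1).
3. Give serious TEAEs and AESIs by lot as counts only (SAP 7.2.3 and 7.2.4).
4. Amend SAP 3.6 and the opening of SAP 7 to allow these columns, and reconcile the study-group wording in the protocol synopsis and 10.6.2 with SAP 3.6, stating which tables are by lot and which are pooled.

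The cost is programming and wider tables; no new data or alpha is needed. The downside is that some lot differences will arise by chance across many reactions and vaccinations. A table note should say that the lot columns are descriptive and that rare-event rates by lot are imprecise.

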3.7 Coding Dictionaries

Medical history and AEs will be coded to system organ class and preferred terms using the current version of Medical Dictionary for Regulatory Activities (MedDRA) dictionary version 22.0.

Medications will be coded according to the latest version of the World Health Organization’s (WHO) WHODrug Global Dictionary version prior to the database lock.

3.8 Toxicity and Severity Grading Scales

The toxicity grading scales (Grade 1 to 4) that will be used for safety assessment in this study are presented in **Protocol EBS.AVA.212, Appendix A** (Table 8 and Table 9), based on the FDA Guidance for Industry: *Toxicity Grading Scale for Healthy Adult and Adolescent Volunteers Enrolled in Preventative Vaccine Clinical Trials* (CBER, 2007). The severity of AEs, vital signs, and reactogenicity events will be assessed by the PI or the designee. Clinical laboratory results will be graded by the central laboratory for analytes appearing in **Protocol EBS.AVA.212, Table 9**, reviewed by the PI or the designee. The toxicity grading scale has specific grading options for some clinical symptoms, such as nausea/vomiting, diarrhea, headache, fatigue, and myalgia. For symptoms not appearing on the grading scale, the grading for generic “illness or clinical AE” will be used (refer to **Protocol EBS.AVA.212, Table 8**). For reactogenicity assessment, a Grade of 0 will be available in the e-diary to record “symptom not present”.

4 STATISTICAL ANALYSIS

4.1 General Considerations

All safety analyses will be performed based on the Safety population, and all the immunogenicity and lot consistency analyses will be based on the PP population.

Data summaries will be tabulated by treatment group as specified in Section 3.6. Continuous variables will be summarized by descriptive statistics including number of non-missing observations (n), mean, standard deviation (SD), median, minimum and maximum; categorical variables will be summarized by the frequency count (n) and the percentage of participants (%) in each category.

All clinical laboratory data and vital sign data will be reported using standard international units, if applicable. The immunogenicity response TNA NF₅₀ is a unitless quantitative result as it is derived from ED₅₀ divided by the reference standard of ED₅₀.

The reporting conventions in Appendix I will be applied to all tables, listings, and figures, as appropriate.

All statistical analyses will be performed using SAS® v9.4 or later version.

4.2 Precision

Safety variables (i.e., clinical laboratory values, vital signs) including derivations thereof will be reported to the same precision as the source data. The immunogenicity response TNA NF₅₀ will be reported with one decimal place or two significant digits (e.g., 0.032, 18.0).

4.3 Derived Variables

Study Day 1 is defined as the day of the first vaccination (same as the day of randomization). The day prior to Study Day 1 is Day -1. There is no Day 0.

In all data listings, study day relative to Study Day 1 will be presented. Study day relative to Study Day 1 will be calculated as:

- study day = (assessment date – date of first vaccination) if the assessment is before the date of first vaccination.
- study day = (assessment date – date of first vaccination + 1) if the assessment is on or after the date of first vaccination.

4.4 Handling of Missing Data

Unless otherwise specified, no imputation will be made for missing data.

Immunogenicity response TNA NF₅₀ values which are below the lower limit of quantification (LLOQ) will be handled according to the specifications in Section 6.

Participants in the PP Population who have missing immunogenicity data at Day 29 will be excluded from Day 29 immunogenicity analysis, with the assumption that the missingness is

completely at random since the participants will not have any knowledge about their immune response in terms of TNA NF₅₀.

Descriptive safety presentations will be based on observed cases. To permit proper tabulation of AEs or medications, if appropriate, the following conventions will be used for imputation of completely and partially missing dates:

- For start date missing completely, impute the date of first vaccination
- For start date with missing day only, impute the 1st of the month unless month is same as month of first vaccination then impute the date of first vaccination.
- For start date with missing month and day, impute 1st January unless year is the same as the date of first vaccination then impute the date of first vaccination
- For end date missing completely, impute date of last contact
- For end date with missing day only, impute the last day of the month. If the month of the end date is same as month of last contact then impute the date of last contact
- For end date with missing month and day, impute 31st December or date of last contact, whichever is earlier
- If the end date is not missing and the start date is after the end date after missing value calculation, the end date will be used for the start date.
- An AE with completely missing both start and end dates, or with the start date missing and end date later than the date of first vaccination, will be considered to be treatment- emergent.

Missing start/end dates will appear as missing in the participant data listings.

Unless otherwise specified, no other imputation will be made for missing data.

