- For WOCBP, confirm continued use of an adequate method of contraception and inquire about any possible pregnancies (refer to [Section 9.3](#))
- Record medications taken since the last visit or contact (if related to AE, SAE and/or AESI)
- Review the status of ongoing AEs/SAEs/AESIs to update the resolution status

During the telephone calls, the staff member is to inquire about and record in source documentation any AEs and SAEs occurring since either the Day 64 visit or the preceding phone contact. Any occurrence of SAE will be reported to Emergent immediately as specified under [Section 9.3](#) and followed up per procedures described in [Section 9.6.2](#). If an SAE has occurred, it will be recorded on the AE eCRF with any medications taken also recorded on eCRFs.

During the telephone calls, the staff member will also attempt to elicit and record in source documentation any information on AESIs of potential autoimmune etiology. If the condition is a diagnosed or suspected AESI, the staff member may refer the participant to the PI or designee for further phone evaluation if needed; based on initial assessment of potential AESI, the participant will be asked to return for an unscheduled clinic visit for evaluation (refer to [Section 8.1.8](#)) and to provide a blood sample for auto-antibody testing and/or TSH assessment (if applicable). The PI or designee will obtain records confirming the diagnosis or refer the participant to a medical specialist for additional clinical and diagnostic testing and follow up until the diagnosis is ascertained. The potential AESI will be reported to Emergent immediately as specified in [Section 9.3](#) and followed up per procedures described in [Section 9.6.2](#). Only after the DSMB has assessed the case as a confirmed AESI will the PI or designee record the occurrence of the AESI on the AE eCRF with any medications taken also recorded on eCRFs. The MM or designee will direct the completion of the AE eCRF when communicating the DSMB assessment outcome(s) to the PI or designee.

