2.3.2 Secondary Endpoints

The secondary study endpoints are as follows:

Immunogenicity:

- Lower bound of the two-sided 95% CI will be $\geq 67\%$ for the proportion of AV7909 participants in Groups 1-3 (three lots pooled) achieving a TNA NF₅₀ ≥ 0.15 on Day 29.

Safety:

- Incidences of AEs from the time of the first vaccination on Day 1 through Day 64.
- Incidences of clinical laboratory abnormalities.

- Incidences of autoimmune-associated AESIs from the time of the first vaccination on Day 1 through the 12-month safety follow-up telephone call following the last vaccination.
- Incidences of solicited systemic reactions and solicited injection site reactions by severity following each vaccination as reported in participant e-diaries.

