7.2.2 All TEAEs

All TEAEs will be summarized by SOC and PT in descending order of participant incidence in AV7909 group (three lots pooled).

TEAEs that occurred in 1% or more for a PT term in either AV7909 group or BioThrax group will be tabulated by SOC and PT.

All TEAEs will be summarized by severity to IP, SOC, and PT for AV7909 (three lots pooled) and BioThrax group. All TEAEs will be summarized by relationship to IP, SOC, and PT for AV7909 (three lots pooled) and BioThrax group. Participants having the same TEAE more than once will be counted once for each PT and once within each SOC at the maximum severity and relatedness. If the severity/relatedness is missing for one or more of the occurrences, the maximum severity/relatedness of the remaining occurrences will be used.

For the analysis purpose of one of the secondary safety endpoints, the incidences of AEs from the time of the first vaccination on Day 1 through Day 64, where so indicated, selected

AE summaries will be provided for all TEAEs and for TEAEs reported during study period Day 1 to Day 64, respectively.

A participant data listing of all AEs (including treatment-emergent AEs (TEAEs) and non-TEAEs) sorted by site, study group, subject ID and AE start date/time will be provided. This listing will include a “Treatment-emergent” flag. Separate listing will be provided for Grade 3 or 4 TEAEs.

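### SAP 4.4 dates incomplete AE onsets to the earliest possible day, with no lower limit from the last contact; if the Day 1–64 AE tables use those dates, some later events are counted there

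*SAP*

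**What the plan says.** SAP 4.4 introduces its date conventions with "To permit proper tabulation of AEs or medications, if appropriate" and gives three rules for an AE start date:

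- No date at all: "For start date missing completely, impute the date of first vaccination".
- Day missing: "impute the 1st of the month unless month is same as month of first vaccination then impute the date of first vaccination". The comparison is of months; the year is not mentioned.
- Month and day missing: 1 January "unless year is the same as the date of first vaccination then impute the date of first vaccination".

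One correction follows. It applies "If the end date is not missing and the start date is after the end date after missing value calculation", and then the end date becomes the start date. That can only move a start earlier. No rule refers to the date of a visit or call.

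The secondary safety endpoint in SAP 2.3.2 is "Incidences of AEs from the time of the first vaccination on Day 1 through Day 64". SAP 7.2.2 implements it by saying that "AE summaries will be provided for all TEAEs and for TEAEs reported during study period Day 1 to Day 64, respectively". It does not say whether the recorded onset, the imputed onset or the date of reporting puts an event in that period. SAP 7.2.1 uses the start date for the treatment-emergent flag.

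Under Protocol 8.1.8, staff at the calls from Month 4 on are to "inquire about and record in source documentation any AEs and SAEs occurring since either the Day 64 visit or the preceding phone contact". Protocol 9.7.1 has new nonserious AEs collected up to the Month 13 call, and SAP 2.2.3.1 also has AEs recorded to Month 13.

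**The concern.** Dating an incomplete onset as early as possible is sensible for deciding whether an AE is treatment-emergent, because doubt then counts against the vaccine. The same dates serve less well for deciding whether an AE belongs to Days 1–64, since every error runs towards the earlier period. An AE first mentioned at the Month 7 call with only the year recorded becomes an AE on the day of first vaccination if that is the vaccination year.

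The plan also sets aside information that it collects. A call asks about the time since the previous contact, so an event first reported there would be expected to have begun after that contact. At stake is a descriptive secondary endpoint: Day 1–64 incidence could be somewhat too high, and some late events would appear to start on Day 1.

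**Working it through.** The documents give no rate of incomplete dates and no figure on this point, so there is nothing to reproduce. The check applies the SAP 4.4 rules to known onsets and counts how many change period.

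**Rules.** Let v be the date of first vaccination, o the true onset and i the imputed start. Study day is the date minus v, plus 1 (SAP 4.3).

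- No date: i = v.
- Day missing: i = v if o and v share a calendar month, otherwise the 1st of o's month. This was run literally (month only) and with the year also required to match.
- Month and day missing: i = v if o and v share a year, otherwise 1 January of o's year.

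An AE is misplaced if o is Day 65 or later and i is Day 64 or earlier.

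**Assumptions.** Onset is uniform over Days 65–394. First vaccinations are spread evenly over either all of 2019 or 15 March to 11 August 2019. The shorter span reflects the Protocol synopsis: about 20 months in total less about 15 months per participant leaves about 5 months for enrolment. The calendar dates are assumed.

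**Result, if the tables use imputed onset** (share of onsets on Days 65–394 placed in Days 1–64):

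| Missing part | Full-year span | 5-month span |
|---|---|---|
| Whole date | 100% | 100% |
| Month and day | 54.7% (37.7% to Day 1) | 46.5% (all to Day 1) |
| Day, year checked | 4.5% (none to Day 1) | 4.5% (none to Day 1) |
| Day, literal rule | 13.7% (9.2% to Day 1) | 13.7% (9.2% to Day 1) |

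If the tables use the date of reporting, every entry is 0%.

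**Where the year-only shares arise** (5-month span): 100% of onsets on Days 65–120, 82.8% on Days 121–211, 24.3% on Days 212–302 and 0% on Days 303–394. Weighted by days, (56×100 + 91×82.8 + 91×24.3 + 92×0)/330 = 46.5%.

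**Hand check of the day-missing shares.** With the year checked, an AE moves only if its onset lies in the calendar month that contains Day 64. The average number of days left in that month after Day 64 is (7×465 + 4×435 + 378)/365 = 14.7. That is 14.7/30 = 49% of onsets on Days 65–94, 14.7/56 = 26% on Days 65–120 and 14.7/330 = 4.5% on Days 65–394. None move after Day 120. The literal rule adds the vaccination month one year later: about 33.0% of the 92 days from Day 303 to Day 394, or 92×0.330/330 = 9.2%. The sum is 4.5 + 9.2 = 13.7%.

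**Examples**, with first vaccination on 10 May 2019, so that Day 64 is 12 July:

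- Only 2019 recorded, true onset Day 115: imputed to Day 1, moved in.
- Only 2020 recorded, true onset Day 297: imputed to Day 237, stays out.
- July 2019, true onset Day 72: imputed to Day 53, moved in.
- September 2019, true onset Day 134: imputed to Day 115, stays out.
- May 2020, true onset Day 377: imputed to Day 1 on the literal rule, moved in; Day 358 if the year is checked, stays out.

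**The case against.** The strongest reply is that the SAP never says that the Day 1–64 tables use imputed onset. SAP 7.2.2 speaks of events reported in that period, and on a report-date reading nothing moves. This stands as a limit on certainty. Imputed onset is still the likelier reading: the conventions exist for tabulating AEs, the treatment-emergent flag runs on start date, no report-date variable is defined, and the same SAP 7.2.2 sentence ties the tables to an incidence endpoint.

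The second reply concerns how many events are exposed. Protocol 9.7.2 names only confirmed SAEs and confirmed AESIs for eCRF recording from Day 65, and those should usually come with documented onset. Protocol 9.2 and 9.7.1 and SAP 2.2.3.1 describe wider collection, so the documents leave this open. Quarterly calls and the query process in Protocol 11.3 should also make year-only dates uncommon. Both points reduce the likely number without removing the problem.

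Third, the percentages describe incompletely dated events, not the endpoint. Participants are counted once per preferred term, so a moved event matters only if the participant had no such event already in Days 1–64. That is correct.

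A reader might infer that late-reported AEs in general drift into Days 1–64, or that the comparison with BioThrax is distorted. The documents do not support either. Complete dates never move, and most day-missing dates do not. The same rule applies to both groups, and Protocol 10.6.2 plans no formal testing of AEs.

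**Conclusion.** The point holds in limited form. Applied as written, SAP 4.4 can place an AE with onset after Day 64 in Days 1–64, and among AEs with true onset after Day 64 the error is always in that direction. This is conditional on the tables using imputed onset, which is probable but unstated.

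The size depends on what is missing: every such AE with no start date, roughly half of year-only dates, and about one in twenty day-missing dates, or about one in seven on the literal month rule. These shares assume uniform onset and 2019 enrolment. The count of affected AEs cannot be derived, because the documents give no frequency of incomplete dates. It is probably small.

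The treatment-emergent flag, the all-TEAE tables to Month 13, and the SAE and AESI endpoints do not change. This is a minor correction, worth making because the wording is easy to repair.

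**What to change.** Make three changes to the SAP:

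1. Keep the 4.4 rules for the treatment-emergent flag, but require the same month and the same year before a day-missing date is set to the date of first vaccination.
2. State in 7.2.2 that the Day 1–64 tables go by onset date.
3. Add that an AE first reported after the Day 64 visit with a missing or partial start date is not counted in Days 1–64 unless the recorded part of the date, or an end date, shows onset on or before Day 64.

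For true onsets after Day 64 that are first reported after the visit and correctly recorded as far as they go, the misplaced share then becomes 0% for every pattern, because no recorded month, year or end date could show earlier onset. A simple floor at the day after the last contact would be weaker. It could override a recorded month that lies wholly before Day 64, and a visit held on Days 61–63 (SAP 3.3 allows Days 61–67) would leave the floor inside the period.

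The cost is a few sentences and minor programming. A few events forgotten at the Day 64 visit and recalled later without a full date would be left out of the Day 1–64 tables; they would still appear in the tables to Month 13. The contact at which each AE was first reported must be available. Protocol 8.1.8 puts call findings in source documents, but the documents do not show that the AE eCRF holds this item, so it should be confirmed. The SAP should also say how participants without a Day 64 visit are handled.
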